## List of Abbreviations

3MH	3-methyl-d3-L-histidine stable isotope
AMDR	acceptable macronutrient distribution range
ANOVA	analysis of variance
AUC	area under the curve
BMI	Body mass index
CRF	Case Report Form
D2O	Deuterated water
DXA	Dual-energy X-ray Absorptiometry
EAA	Essential Amino Acid
GC-MS	Gas chromatograph-mass spectrometry
IRB	Institutional Review Board
MPS	Muscle protein synthesis
NB	Net balance (of protein metabolism)
NHANES	National Health and Nutrition Examination Survey
OPI	Optimal Protein Intake
PS	Whole-body protein synthesis
PB	Whole-body protein breakdown
RDA	Recommended Daily Allowance
RIOA	Reynolds Institute on Aging
UAMS	University of Arkansas for Medical Sciences

## Study Schema

Recruiting will be performed via word of mouth, TRI subject database (ARresearch.org), and the UAMS social media platforms.

Visit 1: informed consent process takes place at the RIOA. Enrolled subjects undergo body composition test and DXA scan (or at Visit 2) using PI's equipment.  
Randomization (1:1:1) occurs.

Visit 2: subjects undergo body composition test and DXA scan if not done at Visit 1.  
Run-in meals are dispensed.

Visit 3: Subjects report fasted to the RIOA to begin a 13-hour visit that entails stable isotope ingestion, blood/urine/saliva sampling and study meal ingestion.

Visit 4: Subjects report fasted to the RIOA the morning after visit 3 to undergo blood, saliva, urine and muscle sampling approximately 24 hours after isotope ingestion.

**Study Calendar**

Procedure	Visit 1	Visit 2	Visit 3	Visit 4
Informed consent	X			
DXA scan	X 	X		
Body composition testing	X 	X		
Randomization	X			
Pick up run-in meals		X		
24-hour stable isotope procedure			Start	Finish

Or at Visit 2.

**1.0 Protocol Summary**

This will be a randomized study to demonstrate how animal-based protein-rich food sources can be used by older adults to increase protein intake within pre-existing dietary patterns. In this regard, we propose to augment the current dietary pattern of older Americans by readily available quality protein sources. To this end, we will investigate the effects of recommended and common protein intakes on the maintenance of whole-body protein balance and potential for muscle protein anabolism. Plans to accomplish project goal(s): We will study 3 groups of 10 older subjects during daily protein intakes of 0.8 (recommended dietary allowance [RDA]), 1.1 (National Health and Nutrition Examination Survey [NHANES]), and 1.5 (optimal [OPI]) g/kg/d. Due to common eating patterns in older adults (1), these protein intakes will be structured within 2 meals per day. A 2-day dietary lead-in (matching the subject's intervention paradigm) will proceed each dietary intervention. Whole-body protein balance will be determined during metabolic study days by oral ingestion of 2 grams of the stable isotope N-alanine, and a 24-hr integrated value of muscle protein synthesis will be determined by ingestion of deuterated water. Oral ingestion of 10mg of 3-Methyl-d3-L-histidine and analysis of urine samples will permit measurement of muscle protein breakdown during this period. Integrated post-meal blood EAA will also be determined, as we have demonstrated a relationship between peripheral EAA response and protein anabolism.

Study duration per subject will be about 2 weeks.

---

## 2.0 Background

---

### 2.1 Rationale and Significance

Sarcopenia is the age-related loss of skeletal muscle mass and function. Sarcopenia is a complex multifactorial syndrome associated with increased risk of morbidity, mortality, and healthcare cost. Despite being associated with advanced age groups, the loss of skeletal muscle mass and function begin in the third and fourth decades of life, respectively (2). Thus, treatments that prevent age-related losses of skeletal muscle mass and function are essential for all aging populations.

Protein turnover is an important regulatory process of muscle growth and function and is influenced by daily protein intake in order to supply precursor amino acids to activate protein synthesis and attenuate protein breakdown. The current RDA for protein for adults is 0.8 g/kg/d, which is the minimum protein intake necessary to avoid malnutrition (3). However, the acceptable macronutrient distribution range (AMDR) was developed to express dietary recommendation in the context of a complete diet. For protein the AMDR is 10 – 35% of total calories. Assuming a 2000 Kcal healthy US-style eating pattern, the AMDR provides 1.05 – 3.67 g/kg/d when reference body weights of 57 and 70 kg are assumed for women and men, respectively (4). In this regard, even the lower end of the AMDR intake is higher than the RDA. Moreover, many nutritional organizations (3,5) have recommended intakes above the RDA (1.2 - 2 g/kg/d) for older adults. Despite this level of support, an increase in the RDA for the general population, or for older adults, has not materialized.

[figure not shown]
Increasing the RDA would represent a physiologically accurate acknowledgment of an increased protein requirement with aging. The adequacy of protein intake is made further difficult as older adults tend to consume lower food/caloric intakes as they age. This age associated decrease in food/caloric intake has been attributed to reduced appetites, changes in chemo-sensory abilities, and deteriorations in dentition, manual dexterity, and gastro-intestinal function (6). Unfortunately, studies suggest that the consumption of animal-based protein-rich foods is impacted to a greater degree (6).

This is of concern as animal-based protein-rich foods not only provide a better protein to

calorie ratio, requiring less total food intake to meet protein requirements, but also provide unique nutritional profiles that cannot be obtained through supplementation or substitution (7). Furthermore, we have demonstrated (Figure 1) that complete protein ingestion leads to a greater increase in peripheral EAA, and further, that this increase is directly related to the increase in muscle protein synthesis and whole-body net protein balance. It is apparent that the use of animal-based protein-rich food sources are imperative for older adults to meet their elevated protein requirements. Thus, it is crucial to identify nutritional strategies that require minimal changes in eating behaviors of older adults yet improve the potential for protein homeostasis.

Older adults have decreased motor abilities, which impacts their ability to cook and prepare their own food. Animal-based protein-rich food sources often require more time and effort to prepare than plant sources. This aspect contributes to inadequate protein intakes as plant sources have a lower protein to calorie ratio. Thus, an important strategy to increase daily protein intake is to improve the convenience and minimize the effort required to prepare animal-based protein-rich food sources. This can be readily accomplished by using minimally and further processed meat and poultry products within older adults' diet. The reduced effort and time required to incorporate these products into a pre-existing dietary plan would improve the potential of successful implementation.

One common approach to increase dietary protein in older adults has been to define an "optimal" within-day protein intake distribution. Based upon skeletal muscle responses to various doses of protein intake, it was concluded that an even distribution of protein intake, as opposed to an uneven distribution, was preferable (8). The primary issue here is that saturable protein dose limits are not well-defined, and arguably non-existent. Research consistently supports the concept that muscle protein synthesis is maxed out with around 10-15 grams of EAA when supplied in liquid format following resistance exercise (9–13). However, we have observed (Figure 1) that greater protein intake is required when provided in whole-food format as opposed to liquid drinks.

**Figure 1:** A greater digestibility requirement (whole-food protein sources) results in a lower stimulation of muscle protein synthesis. These data also demonstrate that greater peripheral EAA are required to increase muscle protein synthesis.

Basing protein distribution optimization upon saturable protein dose studies reflects the “muscle-full” effect theory, which recently was shown to be an artifact of the rapid and transient rise in circulating amino acids rather than a true physiological effect (14). Furthermore, protein recommendations are based upon whole-body protein requirements, not muscle requirements. This is an important consideration as we (15) and others (16) have demonstrated that whole-body protein balance does not plateau with protein intake; i.e., greater improvements in whole-body net protein balance are observed with increasing doses of protein.

The above highlight an incorrect underlying assumption of evenly distributing protein intake throughout the day. More pertinent to the issue is that studies directly testing protein distribution do not provide strong evidence for an even protein distribution being superior to an uneven protein distribution. Despite some promising data (17) in younger adults ( $36.9 \pm 3.1$  years of age), our recent studies (18,19) in older adults (50 – 75 years of age) demonstrated no superior effect of an even protein distribution on whole-body protein balance or muscle protein synthesis over a 24-hour period. More importantly,

our work indicated that total protein intake throughout the day has a direct influence on anabolism (18–21). The take home message from these studies is that total protein intake, not intake patterns, dictates protein homeostasis. This is an important message, as NHANES data indicates that only 17.3% of adults eat more than two meals a day containing  $\geq 30$  grams of protein per meal (1). Thus, the issue becomes one of increasing protein intake in older adults within their pre-existing dietary patterns. Incorporating minimally and further processed meat and poultry products into current dietary patterns provides an easily accessible strategy for older adults to meet higher protein requirements required to maintain protein mass. Therefore, demonstrating the efficacy of these products to meet body protein demands within a preexisting dietary pattern of two meals a day is the focus of this project.

---

### **3.0 Hypothesis**

---

We hypothesize a stepwise increase, RDA<NHANES<OPI, in muscle protein synthesis and whole-body protein balance with increasing doses of daily protein intake.

---

### **4.0 Study Population**

---

Up to 50 subjects of any gender or ethnicity will be enrolled with a target of n=30 for study completion. Subjects' duration of participation is approximately 2 weeks.

#### **4.1 Inclusion Criteria**

1. Men and post-menopausal women.
2. Ages 50-70 years.
3. BMI  $\leq 35$  kg/m^2.
4. Capable of providing informed consent.
5. COVID-19 negative and/or asymptomatic.

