#### **4.2 Exclusion Criteria**

1. Subject who does not/will not eat animal protein sources.

2. Body mass index >35.
3. Complete blood count lab results that indicate anemia or abnormal white blood cell counts.
4. History of chemotherapy or radiation therapy for cancer in the 6 months prior to enrollment.
5. Use of insulin to control blood sugar level.
6. Currently receiving androgen (e.g., testosterone) or anabolic (e.g., GH, IGF-I) therapy.
7. Currently using prescription blood thinning medications.
8. Unable or unwilling to suspend aspirin use for 7 days prior to Visit 3.
9. Unwilling to avoid using protein or amino-acid supplements during participation.
10. Subjects who are unwilling to fast overnight.

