## 5.0 Study Visits

---

Subjects will be required to wear a mask. If they do not have one, a mask will be provided to them by the study staff.

Visit 1: This visit will take place at the UAMS RIOA. At this visit, informed consent discussion will be held. This visit is expected to take less than one hour. If a subject consents, their height and weight will be measured to determine their BMI. Questions will be asked about their medical history and medication use. Eligible, enrolled subjects will be shown a menu of the foods they will be asked to eat to elicit any food allergies or intolerances. If the subject is fasted for 8 hours, has not had caffeine in 12 hours, and has not strenuously exercised in 24 hours, they will undergo body composition testing and DXA scan. If these criteria cannot be met during this visit, subjects will perform these two tests at Visit 2. A blood sample will be drawn for Complete Blood Count (Labcorp). Randomization will occur. Future study visits are scheduled.

[figure not shown]
Visit 2: This visit will occur in a fasted state if the subject did not meet the body composition testing criteria at visit 1. Subjects will undergo body composition testing and DXA scan. Study meals eaten during the 2-day run-in phase will be dispensed. A

10mg dose of 3MH will be provided with instructions to mix it with water, ingest it at 1900, and record the time on the evening prior to study visit 3. Subjects are instructed to eat all of the provided food and add nothing but non-caloric seasonings and condiments. They may have their usual beverages but must not ingest any protein or amino acid supplements during this time. This visit will take place at the UAMS RIOA.

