Visit 3: This visit will take place at the UAMS RIOA on the morning after subject completes the 2-day run-in meals. At this visit, subjects will report having fasted for 10 or more hours. This visit is expected to take about 13 hours. During this visit, subjects will be asked to provide blood/urine/saliva samples. They will ingest deuterated water (~3mL per kg body weight) at specific times (total dose divided into 10 aliquots and ingested every hour up to study hour 9:00) and 2g of a stable isotope of alanine (15N-alanine) dissolved in water. Two (group-specific) study meals will be served, one in the morning and one in the afternoon/evening. See **Figure 2** for a timeline. After the second saliva sample has been collected, subjects will go home and return to the study site the following morning having fasted overnight.

Visit 4: This visit will take place at the UAMS RIOA on the morning after visit 3. Subjects will fast overnight between visits 3 and 4. Approximately 24-hours after isotope ingestion, the final biological samples will be collected and the subject offered a snack and beverage. They will then be dismissed.

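### Inclusion criterion 5 joins its two COVID-19 conditions with *and/or*, so as written it admits a known-positive person without symptoms and a symptomatic person with a negative test

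*Combined protocol and SAP*

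**What the plan says.** Section 4.1, item 5, sets the only COVID-19 condition for entry: "COVID-19 negative and/or asymptomatic". It does not say how or when either half is established.

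Three other places bear on it:

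- **Exclusions (section 4.2).** None of the ten items names a positive test, symptoms or acute illness. The nearest is item 3: "Complete blood count lab results that indicate anemia or abnormal white blood cell counts".
- **Visit 1 (section 5.0).** "Questions will be asked about their medical history and medication use", and "A blood sample will be drawn for Complete Blood Count (Labcorp"). No COVID-19 test or symptom check is described here, at a later visit or in the study calendar.
- **Protection during visits (section 5.0).** "Subjects will be required to wear a mask". Of Visit 3 the protocol says "This visit is expected to take about 13 hours". It also says "Two (group-specific) study meals will be served, one in the morning and one in the afternoon/evening", and the deuterated water is taken as a "total dose divided into 10 aliquots and ingested every hour up to study hour 9:00".

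**The concern.** An entry rule of this kind exists to keep people who may be infectious out of the clinic. The connective *and/or* makes each condition sufficient alone, so the rule stops only someone who is both positive and symptomatic. Staff who apply the text as it stands could enrol a volunteer who reports a positive test but feels well, or one with cough and fever and a negative test.

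The mask requirement shows that the authors took transmission seriously. Yet the longest visit is built around activities that need the mask off. The first matter at stake is therefore the safety of staff and of anyone else in the room.

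The second is data quality. Whole-body synthesis and breakdown come from one 24-hour urine collection (section 9.2), and muscle synthesis from a single biopsy (section 9.4). No turnover measurement before the diet is described, so a subject who is unwell on that day has no earlier value of their own for comparison.

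**Working it through.** No power, alpha or event-count figure bears on this point, and the plan states no figure to reproduce. The check is a reading of the rule, followed by a search of the rest of the document for anything that closes the gap.

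**Step 1. Criterion 5 as written and with both conditions required.**

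| Test status | Symptoms | As written (either suffices) | Both required |
|---|---|---|---|
| Negative | None | Eligible | Eligible |
| Negative | Present | Eligible | Not eligible |
| Positive | None | Eligible | Not eligible |
| Positive | Present | Not eligible | Not eligible |

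As written, one of four combinations is barred. With both required, three are. The two middle rows are the gap. Eligible here means on this criterion; the other criteria must still be met.

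**Step 2. Does anything else exclude the two middle rows?**

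- Section 4.2, item 3: a white cell count may catch some infected people, but it is drawn once, at Visit 1, and depends on neither test result nor symptoms.
- Section 5.0, Visit 1: general history and medication questions, with no rule attached for COVID-19.
- Section 11.6: staff ask about adverse events at visits, and the investigator and study physician review them. No rule for postponing a visit follows.
- Section 12.0: a general commitment to institutional policies. No COVID-19 procedure is cited.
- Sections 1.0 and 4.0: participation lasts about 2 weeks, so status at Visit 1 need not hold at Visit 3.

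None of these closes the gap.

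**Step 3. Can the mask rule stand in for the criterion at Visit 3?** The occasions that need an uncovered mouth are 2 meals, 10 deuterated-water aliquots, 1 alanine drink and 2 saliva samples (section 5.0 sends subjects home after the second; section 8.3 gives three over Visits 3 and 4).

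2 + 10 + 1 + 2 = 15 occasions at most, fewer if some coincide.

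Hourly aliquots from hour 0 to hour 9 make 10, so the mask comes off at least once an hour over that stretch. The protocol writes no mask exception. That the mask comes off is an inference, but these acts cannot be done with it on.

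**Step 4. When must a second check fall?** Section 5.0 has the subject take the 10 mg 3MH tracer at home at 1900 on the evening before Visit 3. A check made only on arrival at Visit 3 would come after that dose, and a postponement then would mean a tracer dose already taken. The check therefore has to precede the evening dose.

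**The case against.** **The authors probably meant negative if tested, otherwise asymptomatic.** This is plausible, since the protocol describes no test and an alternative for untested people makes sense. Nothing suggests an intention to enrol known-positive people. But the text does not state that reading, and staff must apply what is written. What stands is that this is faulty wording, not a deliberate choice.

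**Partial safeguards exist.** The blood count, history questions, adverse-event questions and institutional policies each offer something, and site screening may exist that the protocol does not show. They reduce the practical risk, but none is an eligibility or postponement rule for COVID-19.

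**A reader might infer that other volunteers are exposed.** The documents do not say that subjects are studied together, so this is not supported. Staff are certainly present; beyond them one can say only anyone else in the room.

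**A reader might infer that one ill subject distorts an arm of 10.** This is not supported either. The documents do not say that infection alters protein turnover, nor by how much. Suppose, purely as an assumption, a shift of 1 to 2 SD in one subject:

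- Shift in the group mean: (1 to 2)/10 = 0.1 to 0.2 SD.
- Standard error of a mean of 10: 1/√10 = 0.32 SD, so the shift is about 0.3 to 0.6 of one standard error.
- Rise in that arm's expected variance: d²/n = 1/10 to 4/10 = 10% to 40%. Pooled over three equal arms, this is about 3% to 13%.

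Because allocation is randomized and the criterion is the same for all arms, this is noise in expectation, not bias toward an arm. The number of affected subjects may well be zero.

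**Conclusion.** The concern holds as a defect of wording with a safety consequence. Criterion 5 literally admits two kinds of person whom it would be expected to keep out, nothing else in the documents excludes them, and the mask rule cannot cover the meals, drinks and saliva sampling at Visit 3. That conclusion rests on the text alone, plus the inference that those activities are done unmasked.

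The benefit of correcting it is mainly the safety of staff and others present. Avoiding occasional noise in a single-day measurement is secondary and depends on outside knowledge about infection and turnover. With no infection rate and no effect size in the documents, no bias is quantified and none is claimed. The point is still worth acting on because the correction costs almost nothing.

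**What to change.** 1. **Reword criterion 5** so that both conditions must hold: no known current positive COVID-19 test, and no COVID-19 symptoms. No new testing is needed, because an untested person without symptoms still qualifies.
2. **State in section 5.0 when this is asked:** at Visit 1, and again before the evening 3MH dose that precedes Visit 3, so that any postponement comes before the tracer is taken. No visit is scheduled that evening, so a telephone call or a written instruction given at Visit 2 would be needed.
3. **Postpone rather than withdraw.** Randomization has already taken place at Visit 1, so rescheduling keeps the randomized groups intact.

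**Cost.** A small edit, two questions asked twice, and an occasional rescheduled visit. A postponement means repeating the run-in meals and repeating or extending the 7-day aspirin suspension in section 4.2. Symptoms that first appear overnight would still be missed by the evening check. How to handle those on arrival, after the 3MH dose, is for the investigators to decide and write down.

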#### **4.2 Exclusion Criteria**

1. Subject who does not/will not eat animal protein sources.

2. Body mass index >35.
3. Complete blood count lab results that indicate anemia or abnormal white blood cell counts.
4. History of chemotherapy or radiation therapy for cancer in the 6 months prior to enrollment.
5. Use of insulin to control blood sugar level.
6. Currently receiving androgen (e.g., testosterone) or anabolic (e.g., GH, IGF-I) therapy.
7. Currently using prescription blood thinning medications.
8. Unable or unwilling to suspend aspirin use for 7 days prior to Visit 3.
9. Unwilling to avoid using protein or amino-acid supplements during participation.
10. Subjects who are unwilling to fast overnight.

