## **8.4 Muscle**

At Visit 4, qualified and credentialed study staff (M.D. or PA) will perform a vastus lateralis muscle biopsy of the subject's outer thigh using 1% plain lidocaine for anesthesia. Approximately 100mg of muscle tissue will be obtained using a Bergstrom needle. The tissue will be rinsed with normal saline and flash frozen using liquid nitrogen. The sample will be transferred into a labelled cryo tube and frozen at < -60 degrees C in the PI's lab.

---

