### **11.2 Blood Sampling**

Up to 10 mL of venous blood will be drawn during visits 3 and 4 in total. This is less than a tablespoon. The risks of drawing blood include pain, bruising, bleeding, and small chance of infection from the needle sticks. One ~5mL sample will be drawn during visit 1 to determine eligibility.

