### **11.3 Percutaneous Vastus Lateralis Muscle Biopsy**

The risks of this procedure include pain, bruising, bleeding, scar formation, and infection. This procedure will be done using aseptic technique by licensed study staff (MD or PA) after injection of local anesthesia (1% plain lidocaine). Approximately 100mg of tissue will be removed from the vastus lateralis muscle (subject's choice of left or right leg).

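### Exclusion 3 acts on the Visit 1 blood count only for anemia and white cells, so no written criterion keeps a subject with isolated low platelets or a known bleeding disorder from the Visit 4 biopsy (minor safety improvement)

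*Combined protocol and SAP*

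**What the plan says.** All references are to the combined protocol and SAP.

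- **Blood count.** Section 5.0 places it at Visit 1: "A blood sample will be drawn for Complete Blood Count (Labcorp). Randomization will occur". Section 11.2 gives its purpose: "One ~5mL sample will be drawn during visit 1 to determine eligibility".
- **Use of the count.** Exclusion 3 in section 4.2 is the only criterion that refers to it: "Complete blood count lab results that indicate anemia or abnormal white blood cell counts".
- **Drug-related bleeding risk.** Exclusion 7 reads "Currently using prescription blood thinning medications". Exclusion 8 reads "Unable or unwilling to suspend aspirin use for 7 days prior to Visit 3". The protocol does not state why either is there.
- **History.** At Visit 1, "Questions will be asked about their medical history and medication use" (section 5.0).
- **Biopsy.** Section 8.4 describes a vastus lateralis biopsy at Visit 4 by an MD or PA: "Approximately 100mg of muscle tissue will be obtained using a Bergstrom needle". Section 11.3 on the biopsy says: "The risks of this procedure include pain, bruising, bleeding, scar formation, and infection".
- **Order of events.** Section 7.0 has allocation follow the eligibility decision.
- **Oversight.** Section 11.0 makes the principal investigator and study physician responsible for overseeing procedures. It also says that subjects gain no direct benefit.

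**The concern.** The protocol draws a blood count to decide who may take part, and the most invasive step it schedules is a needle biopsy with bleeding among the listed risks. The natural bleeding-related item in a blood count is the platelet count, yet the criterion that uses the count stops at anemia and white cells. The two exclusions that bear on bleeding cover drugs only.

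As a result, a subject who will not stop aspirin is excluded by a written rule. A subject with isolated low platelets, or with a bleeding disorder that they know about, meets every written criterion. What is at stake is the safety of a small number of volunteers who have nothing to gain directly from the procedure. Nothing in the estimation or testing is at stake.

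**Working it through.** This is a check of the text; the protocol states no figure on this point to reproduce.

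**Step 1. Count the criteria that bear on bleeding.** Section 4.1 has 5 inclusion criteria and section 4.2 has 10 exclusion criteria.

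| Subject of the criterion | Number | Which |
|---|---|---|
| Uses the blood count | 1 | Exclusion 3 (anemia, white cells) |
| Drug-related bleeding risk | 2 | Exclusions 7 and 8 |
| Platelets, coagulation or a bleeding disorder | 0 | None |

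**Step 2. Look for a rule elsewhere.** The visit descriptions (5.0), the blood and muscle sampling sections (8.1, 8.4), the risk sections (11.0, 11.2 and 11.3 on the biopsy) and the safety monitoring plan (11.6) contain no platelet limit, coagulation test or check for a bleeding disorder before the biopsy. Section 11.6 deals with recording, reviewing and reporting adverse events, which comes after the fact.

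**Step 3. Work out who is left uncovered.** For low platelets, it is a subject with no anemia, a normal white count, no chemotherapy or radiation therapy in the preceding 6 months (exclusion 4) and no prescription blood thinner. For a bleeding disorder, it is a subject who has one, knows it and still volunteers. Both groups are narrow.

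**Step 4. Place the check in time.** Section 5.0 lists the blood draw and randomization at the same visit, with the sample going to an outside laboratory. The documents do not say when the result returns. Sections 7.0 and 11.2 read together settle the order: the sample serves eligibility, and eligibility comes before allocation. The result therefore has to be in hand before a subject is randomized. Waiting is feasible because the first group-specific material, the run-in meals, is handed out at Visit 2 (sections 4.5 and 5.0).

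**Step 5. Room for an extra screen failure.** Section 4.0 allows up to 50 enrolled for 30 completers, which leaves 50 − 30 = 20 subjects who need not complete.

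**The case against.** The strongest reply is that the gap is already largely covered and that asking for more is preference. A known bleeding disorder is just what a medical history should bring out. The operator is a credentialed MD or PA, the principal investigator and study physician oversee procedures, the principal investigator monitors for subject safety (section 10.3), and the consent discussion sets out the risks (section 12.0). Leaving the remaining cases to clinical judgment is defensible in a small study under IRB review. A low cost of change does not in itself show that something is wrong.

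Much of this stands, and it is why the point is minor. It answers the known-disorder case better than the platelet case, since a subject may not know of a low platelet count. It also leaves the text as it is: nothing says what to do with a low count or a positive bleeding history.

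A reader might infer two stronger things that the documents do not support.

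- *That the protocol would send a subject with low platelets to biopsy.* No section obliges a clinician to go ahead after an abnormal result. The finding is only that no written criterion excludes the subject.
- *That subjects may be randomized before the blood count is read.* The Visit 1 listing could suggest this, but section 7.0 puts the eligibility decision first.

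**Conclusion.** The point holds as a minor safety improvement. Exclusion 3 applied exactly as written admits a subject with isolated low platelets, and nothing in section 4.2 excludes a known bleeding disorder, ahead of an invasive procedure that offers the subject no direct benefit. Existing safeguards reduce the risk without amounting to a written rule.

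No size can be attached. The documents give no frequency of low platelets or bleeding disorders among otherwise eligible volunteers, and none for bleeding complications of the biopsy in such people. A reader might want to multiply an assumed prevalence by the 30 completers, but that would measure how often such a subject is biopsied, not how often one is harmed, and its inputs would have no support in the protocol.

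Endpoints, analysis and power are untouched. The low cost of the remedy is a reason to act, not evidence that the risk is large. The conclusion rests on the wording of the criteria. The low cost also assumes that the laboratory's count reports platelets, because the documents do not list its components.

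**What to change.** 1. Extend exclusion 3 with: or a platelet count below a limit fixed in advance by the study physician. Write the chosen limit into the protocol.
2. Add to section 4.2: known bleeding disorder, established from the Visit 1 medical history.
3. State in section 5.0 that randomization is held until the blood count result has been reviewed against exclusion 3, consistent with section 7.0. If the result does not come back during Visit 1, move randomization in the study schema and calendar to between Visit 1 and the preparation of the run-in meals for Visit 2.

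Applying both criteria before randomization means that an excluded subject is a screen failure, not a loss from an allocated group of 10.

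**Cost.** One amended criterion, one added criterion and one line on timing, with the schedule aligned if needed. No new test is required if the count reports platelets. The downside is an occasional extra screen failure, against the margin of 20 between enrollment and completion.
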